Ongoing subjects will continue to administer the remainder of dispensed vials as per the dose regimen prior to Amendment 4 until their first visit with Study Drug Dispensing after Amendment 4 when they will transition to the fixed dose regimen.

[figure not shown]
The duration of the study could be up to 298 weeks, which includes a 288-week open-label maintenance period and a 70-day follow-up. There is a \pm 3 day window for all study visits. An effort will be made to bring subjects back to their original scheduled visit (calculated from Baseline) if they are out of the visit window.

Efficacy and safety measurements will be performed throughout the study (see Table of Activities, Section 5.3.1). Clinical evaluation will be performed at Baseline, Weeks 4, 8, 12, 24, 36, 48, 60, 72, 84, 96, 108, 120, 144, 168, 192, 216, 240, 264 and 288/Premature Discontinuation and unscheduled Visits. Subjects may undergo an optional endoscopy during Weeks 48, 96, 192, and 288/Premature Discontinuation Visit to assess disease activity and for surveillance per the investigator's discretion.

Treatment of Subjects with a Disease Flare

Criteria for Disease Flare are as follows:

- Subjects with a Baseline Study M10-870 PMS of 0 to 2 who present with a PMS at least 3 points greater than their Baseline Study M10-870 score.
- Subjects with a Baseline Study M10-870 PMS of 3 to 4 who present with a PMS at least 2 points greater than their Baseline Study M10-870 score.
- Subjects with a Baseline Study M10-870 PMS of 5 to 6 who present with a PMS at least 1 point greater than their Baseline Study M10-870 score.
- Subjects who present with a PMS of at least 2 points greater than their PMS at the previous visit and who are not in remission per PMS.

Prior to Amendment 4:

- Subjects with a disease flare who were on 0.6 mg/kg (maximum dose of 40 mg, weight based) eow of adalimumab could receive 0.6 mg/kg (maximum of 40 mg, weight based) ew of adalimumab.
- Subjects with a disease flare who were on 0.6 mg/kg ew of adalimumab could receive 40 mg ew (maximum dose of 40 mg).

Subjects with persistently uncontrolled disease while on adalimumab 40 mg ew (max dose) were to be discontinued from the study.

After Amendment 4:

[figure not shown]
- Subjects who are on 20 mg eow of adalimumab may receive 40 mg eow of adalimumab.
- Subjects who are on 40 mg eow of adalimumab may receive 80 mg eow of adalimumab.

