5.4.2 Discontinuation of Entire Study

AbbVie may terminate this study prematurely, either in its entirety or at any study site, for reasonable cause provided that written notice is submitted in advance of the intended termination. The investigator may also terminate the study at his/her site for reasonable cause, after providing written notice to AbbVie in advance of the intended termination. Advance notice is not required by either party if the study is stopped due to safety concerns. If AbbVie terminates the study for safety reasons, AbbVie will immediately notify the investigator by telephone and subsequently provide written instructions for study termination.

This study may conclude approximately 12 weeks after one of the following criteria have been satisfied:

- Study drug received country and local (if applicable) regulatory approval for pediatric ulcerative colitis and application for local reimbursement has been submitted.
- The Sponsor determined that continuation of the study does not further promote the scientific objective of the study.

Following site notification of upcoming conclusion of study, subjects should return to their next scheduled study visit as specified in the protocol. The termination visit should be conducted in place of their regular scheduled study visit. These subjects are considered as having completed the study.

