8.1.7 Interim Analysis

An interim analysis on safety and efficacy will be performed and reported in a full Interim Clinical Study Report for inclusion of the Study M10-870 data in the submission of applications for regulatory approval of the pediatric UC indication in conjunction with the Study M11-290 results. An interim analysis will be conducted after the last subject completed or discontinued from the M11-290 main study. Additional interim analyses may be performed, as needed.

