All time points and corresponding time windows are defined based on Rx days. The protocol specified visits and corresponding time windows are presented in the table below. Measures will only be displayed at the visits where they were planned to be measured. For example, Mayo score is collected at Weeks 0, 48, 96, 192 and 288/Premature Discontinuation (dependent on availability of optional endoscopy data at these timepoints).

Assigned Visit	Nominal Day	Time Window (Rx Day Range)
Week 0	1	≤ 1
Week 4	29	2 to 43
Week 8	57	44 to 71
Week 12	85	71 to 127
Week 24	169	128 to 211
Week 36	253	212 to 295
Week 48	337	296 to 379
Week 60	421	380 to 463
Week 72	505	464 to 547
Week 84	589	548 to 631
Week 96	673	632 to 715
Week 108	757	716 to 799
Week 120	841	800 to 925
Week 144	1009	926 to 1093
Week 168	1177	1094 to 1261
Week 192	1345	1262 to 1429
Week 216	1513	1430 to 1597
Week 240	1681	1598 to 1765
Week 264	1849	1766 to 1933
Week 288	2017	1934 to 2101

If more than one assessment is included in a time window the assessment closest to the nominal day should be used. If there were more than one observation with equal distance to the nominal day the latest one will be used in analyses. For any given variable, if more

than one measurement exists for a subject on the same day, the average of the measurements will be considered to be that subject's measurement for that day.

Missing Data Handling

In general, missing Baseline and safety data will not be imputed.

Baseline Value is Missing:

Subjects will be excluded from analysis of change from Baseline if Baseline evaluation is missing.

Missing Efficacy and Outcome Evaluations:

The following methods will be used for imputing missing values to perform the efficacy analyses.

[figure not shown]
For interim analyses, missing values will only be imputed up to the timepoint a patient could have potentially reached at the data cutoff for analyses.

Observed Cases (OC): missing values will not be used for the observed case analysis.

Last Observation Carried Forward (LOCF): For categorical and continuous efficacy variables the following rules will be used for LOCF approach:

- Baseline and pre-baseline values will not be used to impute the missing post-baseline values, and
- Missing values after baseline will be imputed using the last non-missing values after baseline and prior to the missing value.

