8.0 Patient Disposition

Subject accountability overall and by current investigator will be summarized with number and percentage of subjects.

[figure not shown]
Subjects with any dose adjustments will be summarized as follows:

- Total number and percentage of subjects with EOW vs EW at Baseline
- Number and percentage of subjects with at least one dose escalation (EOW to EW)
- Number and percentage of subjects with EW dosing (i.e., those who started on EW or who escalated to EW) with at least one de-escalation (EW to EOW)
- Number and percentage of subjects who de-escalated from EW to EOW with at least one re-escalation afterwards (EOW to EW)

Subject final status including the following categories will be summarized by number and percentage:

- Subjects who completed the study (defined as: either completed Week 288 or switched to adult care or to commercial Humira), also by sub-category of completion:
 - Completed Week 288
 - Switched to adult care
 - Switched to commercial Humira
- Subjects who discontinued

In addition, the reasons for premature discontinuation of study drug (primary reason and all reasons) will be summarized with frequencies and percentages. Subjects may have

multiple reasons for prematurely discontinuing study drug, but will be counted only once for the primary reason.

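### All-cause and efficacy-related discontinuation and first dose escalation are planned only as crude percentages over unequal follow-up, so the figures carry no time, move with the data cut, and fall below the Week 288 risk when subjects are censored earlier

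*SAP*

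**What the plan says.** SAP 8.0 (Patient Disposition) sets the metric for three outcomes.

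- Final status: "Subject final status including the following categories will be summarized by number and percentage".
- Reasons: "the reasons for premature discontinuation of study drug (primary reason and all reasons) will be summarized with frequencies and percentages".
- Escalation: "Number and percentage of subjects with at least one dose escalation (EOW to EW" is one of four dose-adjustment lines. No denominator is stated for it.

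Neither document plans a Kaplan-Meier curve, a cumulative incidence, a rate, or a percentage restricted to subjects with a given potential follow-up for these outcomes.

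Several features make follow-up differ between subjects.

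- Each subject enters at the Week 52 visit of the parent study (SAP 4.2), so entry is staggered.
- Protocol 5.1 gives the maximum: "The duration of the study could be up to 298 weeks, which includes a 288-week open-label maintenance period and a 70-day follow-up".
- Protocol 8.1.7 places the interim: "An interim analysis will be conducted after the last subject completed or discontinued from the M11-290 main study". SAP 4.4 says that this report goes into the regulatory submission.
- Protocol 5.4.2 allows an early end: "This study may conclude approximately 12 weeks after one of the following criteria have been satisfied". The criteria are local approval with a reimbursement application, or a sponsor decision.
- SAP 8.0 counts a subject as a completer who "either completed Week 288 or switched to adult care or to commercial Humira", so completion can occur well before Week 288.

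The SAP does allow for unequal follow-up elsewhere. For interim efficacy, SAP 6.0 says that "missing values will only be imputed up to the timepoint a patient could have potentially reached at the data cutoff for analyses". SAP 9.0 summarises exposure duration, and SAP 11.2 gives adverse events, including those leading to discontinuation of study drug, per 100 patient-years.

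**The concern.** The objective is long-term safety, tolerability and maintenance of response. How long children stay on drug, and how many need escalation, bear directly on it. Discontinuation also carries efficacy information, because persistently uncontrolled disease at the maximum dose leads to withdrawal (SAP 4.2).

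A crude percentage mixes subjects followed for years with subjects followed for weeks. It cannot be read as a risk by a stated week. If the interim figure is lower than the final one, the reader cannot tell a change in risk from a change in follow-up. A low interim percentage could be taken as good long-term persistence when it partly reflects short observation.

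**Working it through.** **The plan's own figures.** The documents give no expected discontinuation or escalation rate, so there is nothing to reproduce for the outcome itself. The duration does reproduce: 288 + 70/7 = 298 weeks.

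**Inputs from the documents.** About 55 subjects outside Japan (SAP 4.3); maximum treatment 288 weeks.

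**Assumptions.** Constant hazard h of 0.05 to 0.30 per year. Entry uniform over S weeks, with S = 52, 104, 156 or 220, and the cut at the last entry. The 220-week value is the gap between the original protocol (7 May 2015) and Amendment 3 (30 July 2019), on which the SAP is based. It illustrates a long span; it is not a known entry period. One year is 52.1775 weeks.

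**Formulas.** With F(t) = 1 − exp(−ht), the expected crude percentage is the average of F over each subject's potential follow-up C. For follow-up uniform between a and b:

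crude = 1 − [exp(−ha) − exp(−hb)] / [h(b − a)]

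Since F increases, the average of F(C) cannot exceed F(288 weeks), and it is strictly lower if any subject's follow-up is cut before Week 288. This holds for any increasing F, not only a constant hazard.

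**Worked case.** h = 0.10 and S = 104 weeks = 1.993 years, so hS = 0.1993. Crude = 1 − (1 − 0.8193)/0.1993 = 9.3%.

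**Expected crude percentage, cut at last entry:**

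| Hazard per year | S = 52 | S = 104 | S = 156 | S = 220 | Risk at Week 96 | Risk at Week 288 |
|---|---|---|---|---|---|---|
| 0.05 | 2.5 | 4.8 | 7.1 | 9.8 | 8.8 | 24.1 |
| 0.10 | 4.8 | 9.3 | 13.6 | 18.4 | 16.8 | 42.4 |
| 0.20 | 9.3 | 17.5 | 24.7 | 32.4 | 30.8 | 66.8 |
| 0.30 | 13.6 | 24.7 | 34.0 | 43.3 | 42.4 | 80.9 |

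The crude figure runs from about 10% of the Week 288 risk (2.5/24.1) to about 54% (43.3/80.9). In the 220-week column it slightly exceeds the Week 96 risk.

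**Moving the cut.** With S = 104, a cut 0, 52 or 104 weeks after last entry gives 9.3%, 17.9% and 25.7% at h = 0.10, and 17.5%, 32.4% and 44.6% at h = 0.20. In simulation (n = 55, 3,000 runs, h = 0.10) the mean Kaplan-Meier estimate at Week 96 was 17.0%, 16.8% and 16.9% at the three cuts, against a true 16.8%.

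**Interim against final.** At h = 0.20, follow-up uniform over 0 to 4 years gives 31.2%, and over 2 to 5.5 years gives 51.8%. The hazard is the same in both.

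**What an interim curve could support.** For n = 55, h = 0.20 and follow-up uniform over 0 to 4 years (4,000 runs), about 21 subjects remain at risk at Week 96 and about 2 at Week 192. At Week 192, 94% of runs have fewer than 5 at risk, and the central 95% of estimates runs from about 29% to 78%. Weeks 240 and 288 lie beyond that follow-up altogether.

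**The case against.** The strongest reply is that SAP 8.0 describes disposition and does not claim to estimate risk. Discontinuation and escalation are not among the efficacy endpoints of Protocol 5.3.2 or SAP 10.2, or the safety parameters of SAP 11.1, and all analysis is descriptive. That stands, and it makes this an improvement rather than a correction of an invalid analysis. It does not help a reader who has only these percentages from which to judge persistence on treatment.

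The second reply is that the plan already adjusts in part. That also stands. The rate per 100 patient-years for adverse events leading to discontinuation covers the part closest to tolerability, and the exposure summary shows time on drug. All-cause discontinuation, efficacy-related discontinuation and escalation remain uncovered.

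Third, if switching to adult care or commercial drug is a competing event and no subject is cut off by study conclusion, the final crude percentage is already a cumulative incidence. This is correct, but the SAP does not say how switching is regarded, and Protocol 5.4.2 makes early closure possible.

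A reader might infer more than the documents support.

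- That the crude figure is too low at every time point: the 220-week column shows otherwise.
- That the interim cut falls at the moment the last parent-study subject finishes: the protocol says after, and gives no cutoff date.
- That escalation is divided by all subjects: SAP 8.0 states no denominator there, and the next two dose-adjustment lines use conditional ones.

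**Conclusion.** The point holds in a limited form. For all-cause discontinuation, efficacy-related discontinuation and first escalation, the planned percentages have no time attached, depend on the cut, are not comparable between reports, and lie below the Week 288 risk when follow-up is cut short. The direction follows from the formula. The size does not come from the documents: under the assumed hazards and entry spans, an interim percentage would be about 10% to 54% of the Week 288 risk.

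It would be wrong to conclude that the plan ignores follow-up time throughout, or that the interim figures understate risk at all weeks. No hypothesis test, error rate or power is involved. This is a cheap improvement.

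**What to change.** Keep the SAP 8.0 counts and add the number of subjects ongoing at each cut. Then add the following.

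1. Cumulative incidence at fixed weeks (for example 48, 96, 144, 192, 240 and 288) with numbers at risk and 95% CI, shown only where enough subjects remain at risk. Set that minimum in advance. At the interim the later weeks will probably be blank.
2. Kaplan-Meier for all-cause premature discontinuation, censoring at data cutoff or study conclusion. Protocol 5.4.2 treats subjects ended by study conclusion as completers, but the SAP's completion sub-categories do not list them; align the two.
3. Aalen-Johansen for discontinuation due to lack of efficacy, with other discontinuation as a competing event.
4. A statement of whether a switch to adult care or commercial drug is censored or a competing event, with the other choice as a sensitivity analysis.
5. First EOW-to-EW escalation restricted to subjects who start on EOW, since those entering on EW cannot have this as a first event, with follow-up ended at the Amendment 4 regimen change.
6. Reconciliation of the SAP's EOW/EW categories, written to Amendment 3 (SAP 3.0), with the regimens after Amendment 4, all of which are every other week (Protocol 5.1 and 5.5.1). An EOW-to-EW move has no meaning under those regimens.

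The cost is SAP wording and one more descriptive output, using dosing and discontinuation dates already collected. The downside is wide intervals at late weeks.

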- Study drug received country and local (if applicable) regulatory approval for pediatric ulcerative colitis and application for local reimbursement has been submitted.
- The Sponsor determined that continuation of the study does not further promote the scientific objective of the study.

Following site notification of upcoming conclusion of the study, subjects should return to their next scheduled study visit as specified in the protocol. The termination visit should be conducted in place of their regular scheduled study visit. These subjects should be considered as having completed the study.

Diagnosis and Main Criteria for Inclusion/Exclusion:

Main Inclusion:

- 1. Subject must have successfully enrolled in and completed Protocol M11-290 through Week 52.
- 2. Subject of legal age, and/or parent or legal guardian, as required, has voluntarily signed and dated an Institutional Review Board (IRB)/Independent Ethics Committee (IEC) approved informed consent form, after the nature of the study has been explained and the subject of legal age, and/or Subject's parent, or legal guardian, as required, has had the opportunity to ask questions. The informed consent must be signed before any study-specific procedures are performed. Subjects will be included in all discussions, and if required, their signature on an assent form will be obtained.

Diagnosis and Main Criteria for Inclusion/Exclusion (Continued):

Main Inclusion (Continued):

[figure not shown]
- 3. Parent or legal guardian of subject who is not of legal age, as required, must be willing to actively supervise storage and administration of study drug and to ensure that the time of each dose is accurately recorded in the subject's electronic diary.
 - If a subject is of a legal age, subjects must be able and willing to self-administer SC injections or have a qualified person available to administer SC injections and to ensure that the time of each dose is accurately recorded in the subject's electronic diary.
- 4. If female, subject who is either not of childbearing potential, defined as pre-menstrual, or is of childbearing potential and is practicing an approved method of birth control throughout the study and for 150 days after last dose of the study drug.

Examples of approved methods of birth control include the following (see local informed consent for more detail):

- Total abstinence from sexual intercourse;
- Condoms, sponge, foam, jellies, diaphragm or intrauterine device (IUD);

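### The SAP's definition of study completion omits subjects closed out when the study concludes, whom the protocol counts as completers; those who move to neither adult care nor commercial Humira have no completion route

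*SAP*

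**What the plan says.** **SAP, Section 8.0 (Patient Disposition).** The final-status table is introduced with "Subject final status including the following categories will be summarized by number and percentage". Two statuses follow. The first is completion, defined as having "either completed Week 288 or switched to adult care or to commercial Humira", with one sub-category for each of the three routes. The second is "Subjects who discontinued". The same section then tabulates the primary reason and all reasons for stopping study drug prematurely.

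**Protocol, Synopsis and Section 5.4.2.** The study concludes about 12 weeks after either of two triggers. The first is approval of the drug for children with ulcerative colitis in the subject's country, together with the filing of a local reimbursement application. The second is a sponsor decision, worded as "The Sponsor determined that continuation of the study does not further promote the scientific objective of the study".

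Once a site has been told of the upcoming conclusion, subjects come to their next scheduled visit, and "The termination visit should be conducted in place of their regular scheduled study visit". On their status, Section 5.4.2 says "These subjects are considered as having completed the study", and the Synopsis says "These subjects should be considered as having completed the study".

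**The concern.** The two documents define completion differently, and the SAP leaves out the one early-completion route that the protocol names. Because the termination visit replaces the next scheduled visit, it can fall before Week 288. A subject who stayed on study until the sponsor closed it could then appear in the report as having discontinued, although the protocol says that the subject completed.

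The study's objective is long-term safety, tolerability and maintenance of response, and every result is descriptive. Readers of such an extension look at how many subjects stayed to the end and why the others left. Mixing administrative closure with withdrawals for adverse events or loss of response would make retention look worse than it was. It would also put into the discontinuation-reason table subjects who are not premature discontinuations under the protocol.

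**Working it through.** The plan states no completion rate, so there is no figure to reproduce. The check is a comparison of the two definitions, followed by one line of arithmetic.

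**Step 1. Classify each way of leaving at study conclusion before Week 288.**

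| Subject's course at study conclusion | Protocol 5.4.2 | SAP 8.0 |
|---|---|---|
| Termination visit, then commercial Humira | Completed | Completed (commercial Humira) |
| Termination visit, then adult care | Completed | Completed (adult care) |
| Termination visit, neither of these | Completed | No completion route; the only other listed status is discontinued |

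The documents disagree only in the third row.

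**Step 2. Ask whether the third row can be occupied.**

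- Under the sponsor-decision trigger, nothing implies that marketed drug is available for this use, so no switch can be presumed.
- Under the approval trigger, reimbursement need only have been applied for. Many subjects may move to commercial drug, but the condition does not ensure that all can.
- The approval trigger is a realistic prospect: Protocol Section 5.6.4 describes the fixed-dose regimen as aligned with labelling that is partly approved already and partly anticipated.

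**Step 3. Size per subject.** The denominator is the 55 subjects expected outside Japan (SAP Section 4.3; the Protocol Synopsis gives the same number for the main study). If *k* subjects fall in the third row:

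- shift in completion % = −100 × *k*/55
- shift in discontinuation % = +100 × *k*/55
- for *k* = 1: 100 × 1/55 = 1.8 points

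The documents give no value for *k*. Purely to show scale, an assumed *k* of 5 gives 100 × 5/55 = 9.1 points and an assumed *k* of 10 gives 100 × 10/55 = 18.2 points. Here *k* counts only subjects in the third row, not everyone on study at closure.

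**Step 4. Trace where completer status is used.**

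- SAP Section 5.1 uses the Full Analysis Set for all analyses.
- SAP Section 10.1 handles missing efficacy data by observed cases and LOCF, neither of which refers to completion.
- SAP Sections 9.0 and 11.2 define exposure and treatment-emergent events from dosing and event-onset dates.

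Completer status therefore enters only the final-status table and, through it, the table of reasons for premature discontinuation.

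**The case against.** The case against making much of this has several parts.

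- **Many closed-out subjects are already covered.** Those who go on to commercial Humira or adult care have a completion line in the SAP. This stands, and it removes what may be most of the group under the approval trigger.
- **The SAP never says that closed-out subjects are discontinuations.** The list of statuses is introduced as *including* certain categories, so it is not stated to be exhaustive. This stands in part: the discontinued label is a default inference, not a written rule. But the open wording governs the list of statuses, while the definition of completion is itself closed, with three alternatives. Adding a third status would still leave these subjects outside completion, contrary to the protocol.
- **The reasons table could reveal an administrative closure.** It could, but only by listing as premature discontinuations subjects whom the protocol calls completers.
- **The SAP may simply lag behind the protocol.** It is written to Amendment 3, and the protocol supplied is Amendment 5. The documents do not show whether Amendment 3 held the conclusion rule. The Amendment 5 summary of changes does not mention it, so it does not appear to be new there. This affects how the gap arose, not whether it needs closing.
- **Completion is neither a listed safety parameter nor an efficacy endpoint.** This stands, and it limits the consequence to disposition reporting.

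A reader might also infer that the SAP is wrong to count switches to adult care or commercial Humira as completion. The documents do not support that. The protocol gives no exhaustive definition of completion: a subject who switches at study conclusion is a completer under Section 5.4.2, and on switches made before then the protocol is silent.

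**Conclusion.** The mismatch is real and narrow. Applied as written, the SAP definition denies completer status to subjects who are closed out at study conclusion before Week 288 and move to neither adult care nor commercial Humira, although the protocol states twice that they completed. With the statuses listed, they fall by default among the discontinuations.

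Each such subject costs 1.8 percentage points of completion and adds the same to discontinuation, taking the expected 55 as denominator. The total cannot be stated, because the documents do not say how many subjects will be affected. Two stronger readings should be resisted. One is that everyone on study at closure would be reported as discontinued; this ignores the SAP's two switch routes. The other is that efficacy or safety results are affected; no analysis of either uses completer status.

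The point is still worth correcting, because the SAP gives a rule that contradicts the protocol, and retention is a natural measure of long-term tolerability.

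**What to change.** In SAP Section 8.0:

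1. Add a fourth route to the definition of completion and a matching sub-category, for example *completed at study conclusion (protocol 5.4.2)*.
2. State that subjects in this sub-category are not premature discontinuations and do not enter the table of reasons for premature discontinuation.
3. State that a subject who switches to commercial Humira or adult care at study conclusion remains a completer, and say which sub-category takes that subject, so that nobody is counted twice.
4. Leave switches made before a Section 5.4.2 conclusion visible in their existing sub-categories. The protocol gives no reason to move them.
5. Update the statement of which protocol version the SAP follows, so that the two documents are aligned before database lock.

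The cost is a few sentences of SAP text and one change to the disposition mapping, with no new assessments. This assumes that the end-of-study record, or the date of site notification together with the termination visit, identifies these subjects; the documents do not show the form.
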